One of the most frequently used alternative therapies is herbal medicine that act as anti-ROS agents preventing DNA damage has been used alongside conventional treatment regimens (Li et al, 2016). One of the agents that receives particular strong interest is coffee. Coffee is considered as a major source of dietary antioxidants; some are present in the green bean, whereas others are generated during roasting. Coffee roasting, the process of the heating of green coffee beans transforming them into black coffee beans, transforms the chemical and biological properties of coffee beans (Wei et al. 2012 and Jeong et al, 2013).

Regarding oral cancer, some studies reported an association of high coffee consumption to an augmented risk of oral cancer (Bundgaard et al, 1995 and Franco et al, 1989) while others showed a clear inverse association with the risk of oral cancer (Naganuma et al, 2008 and Hildebrand et al, 2013). Recently, there have been reports of a protective effect of coffee consumption on oral cancer from two recent meta-analysis (Zhang et al, 2015 and Li et al, 2016). To our knowledge, only two studies were done to assess the effect of coffee ingredients (cafestol and kahweol) on oral squamous cell carcinoma cell lines (Chae et al, 2014 and Kotowski et al, 2015).

Due to these controversial findings concerning the effect of roasted coffee and absence of data on unprocessed (green coffee), our study aims to investigate the effect of different coffee beverage as regard apoptosis and proliferation carried out in OSCC cell lines.

Rationale for carrying out this study:

The main objective of our study was to evaluate anti proliferative and apoptotic activity of green coffee, in comparison to roasted coffee and decaffeinated coffee on cultured OSCC cell line.

PICO

Patient / Population: Human Oral squamous cell carcinoma cell line

Intervention1: Green coffee

Intervention2: Roasted coffee

Intervention3: Decaffeinated coffee

Control: no application

Outcome:

Primary outcome 1: assessment of proliferative activity OSCC cell line treated with coffee using **ELISA**.

Primary outcome 2: Assessment of apoptotic cell death of OSCC cell line treated with coffee using **RT-PCR**.

	Outcome measure	Measuring device	Measuring unit
1- Primary1	Proliferative activity	ELISA	Comparative (light absorbed) numerical value
1- Primary2	Apoptotic cell death	RT-PCR	Comparative (fold changes) numerical value

Research question

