Do different types of coffee affect proliferation and/or apoptosis of human oral squamous cell carcinoma cell line?

III. Methods

A) Samples, intervention and outcomes

1) Material:

1. Cell Lines:

Oral squamous cell carcinoma cell line (SCC15), purchased from the confirmatory diagnostic unit, R&D sector, Vacsera, Cairo, Egypt.

2. Coffee extract:

Green coffee, roasted coffee and decaffeinated coffee from local Egyptian market, Cairo, Egypt. The peels and seeds were manually separated.

2) Methods:

Intervention:

Oral squamous cell carcinoma cell line samples will be cultured with and without the addition of green coffee, roasted coffee or decaffeinated coffee extract.

Collecting Samples:

Oral squamous cell carcinoma cell lines will be purchased from (veterinary serum & vaccine research institute, VACSER).

Inclusion Criteria:

Only human cell lines.

Exclusion Criteria:

Animal cell lines.

Mixed tumors.

Sample preparation:

Cells will be sub-cultured in a 96-well plate.

Monolayer cells will be incubated for 48 hours at 37°C in the 5% CO₂ incubator.

After 48 hours, cells will be fixed in wells for 1 hour in trichloro-acetic acid (50%-5 micro liter) which was added to the wells by a multichannel pipette.

Cells will be then washed with tap water and left to dry for 1 hour.

- Sulphorhodamine B stain will be added (50 μ l) and left for half an hour.
- Excess stain will be washed with 5% glacial acetic acid and then attached stain was recovered with EDTA buffer (100 μ l).

Measurements:

a) MTT assay for cellular viability:

1. One ml of cells (50,000-100,000 cells/ml) will be plated into each well of 96-well culture plate for 24 hours before the MTT assay.
2. The cells will be incubated for 24 h in CO₂ incubator.
3. After treatment of cells with antibiotics and antifungal for 24-72 h, experimental media will be removed, and cells will be washed with PBS.
4. Coffee extracts will be added for cell lines with serial dilutions (100 μ g/ml, 10 μ g/ml, 1 μ g/ml, 0.1 μ g/ml, and 0.01 μ g/ml), incubated for 48 hours and then will be washed by PBS twice.
5. The cells will be incubated with medium containing 0.5 mg/ml MTT in CO₂ incubator at 37°C for 4 h.
6. The medium will be aspirated, and the formazan product will be solubilized with dimethyl sulfoxide (DMSO).
7. Absorbance at 570 nm will be measured for each well using a microplate reader (BioTek,Flx 800).

The percentages of cytotoxicity and cell viability are calculated using the following equations:

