% cytotoxicity = 1 - [means absorbance of treated cells/mean absorbance of negative control], % viability = 100 - % cytotoxicity.

Measurement of proliferative activity:

Enzyme assay (ELISA) will be used to estimate the inhibitory effect green coffee, roasted coffee, decaffeinated coffee on **Epidermal growth factor Receptor (EGFR)** protein.

Sample preparation for ELISA:

Cell lysis for cell culture samples will be carried by spinning down cells for 15 minutes at 1200 RPM. Cell pellets are washed once in cold PBS. Cells are re-suspended in Lysis Buffer to a concentration of 1.5x10⁶ cells/mL, are incubated for 1 hour at room temperature with gentle shaking. Cells are centrifuged at 200 x g for 15 minutes. The supernatant will be diluted at least 50-fold in 1X Assay Buffer (5 μ L supernatant + 245 μ L 1X Assay Buffer) for the assay.

1. Prepared biotin antibody is added to samples in different wells.

2. Then prepared Streptavidin horseradish peroxidase (HRP) solution is added after washing.

3. Tetramethylbenzidine (TMB) Solution is added to each well and incubated at room temperature. Stop Solution is added to each well. Readings will be done at 450 nm immediately

Apoptosis activity assay:

Following treatment with green coffee or roasted coffee or decaffeinated coffee for 24 h, the cells are harvested, lysed and tested with RT-PCR using specific primers to estimate the fold change of the gene expression of Caspase-3, bax, bcl-xl and p53.

7. Calculated sample size

No sample size estimation could be done, as the primary outcome is not a measured outcome.

8. Description of study sample

No sample size could be applied on cell line experiments as we generate millions of naturally randomized cells.

9. Intervention for each group

Green coffee extract will be introduced to the 1st group, while roasted coffee will be added to the 2nd group. The 3rd group will be treated with decaffeinated coffee.

10. Outcomes

Apoptosis (Gene expression of Caspase – 3, EGFR).

Prioritization of Outcome	Outcome	Method of measurement	Measuring unit
Primary1	EGFR expression using ELISA	Robonek P2000 ELISA reader	IC 50 µg / ml
Primary2	Caspase-3, bax, bcl-xl and p53 gene expression using RT – PCR	Rotorgene system	Fold change FLD=e-ΔΔCT

B)Assignment to intervention

This study is non-randomized.

11. Sequence generation

Sequence generation is not applied on cell line experiments.

12. Allocation concealment

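### Primary 1 is labelled proliferative activity, but its assay measures EGFR protein at a fixed cell concentration, and the MTT viability assay is in neither outcome table

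*Protocol*

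**What the plan says.** The research question in the Protocol is "Do different types of coffee affect proliferation and/or apoptosis of human oral squamous cell carcinoma cell line". The PICO answers it with two primary outcomes. The first is "assessment of proliferative activity OSCC cell line treated with coffee using" ELISA, with the unit "Comparative (light absorbed) numerical value". The second is "Assessment of apoptotic cell death of OSCC cell line treated with coffee using" RT-PCR, in fold changes.

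The methods say what the assays measure. Under the heading on measuring proliferative activity, "Enzyme assay (ELISA) will be used to estimate the inhibitory effect green coffee, roasted coffee, decaffeinated coffee on" EGFR protein. In the sample preparation for that assay, "Cells are re-suspended in Lysis Buffer to a concentration of" 1.5×10⁶ cells/mL, with no exception by group. Then 5 µL of supernatant goes into 245 µL of buffer. The RT-PCR estimates the fold change of caspase-3, bax, bcl-xl and p53 after 24 h of treatment.

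Section 10 (Outcomes) names Primary 1 as EGFR expression and Primary 2 as expression of the four genes. It gives Primary 1 the unit IC50 in µg/ml. A line above that table places EGFR next to caspase-3 under apoptosis.

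The Measurements section also describes an "MTT assay for cellular viability": five concentrations from 0.01 to 100 µg/ml, 48 h of exposure, and viability and cytotoxicity computed against a negative control. Neither outcome table names MTT, viability or cytotoxicity.

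**The concern.** The label and the measured quantity are different things. EGFR protein per cell is at most an indirect marker of proliferative signalling, and the Protocol gives no argument for using it in place of proliferation. Read by its PICO label, a lower ELISA value would be reported as reduced proliferation even if the cultures grew as fast as control. An unchanged value would be reported as no effect even if most of the cells had gone.

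Primary 2 has the same gap: a change in the mRNA of four genes is not in itself a count of dead cells.

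The assay that does respond to the number of viable cells is fully described but has no stated role, so whether and how it enters the conclusion could be settled after the results are known. The IC50 unit adds to the uncertainty, because it is unclear whether Primary 1 is an EGFR reading, an absorbance or a concentration read from a dose-response curve.

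**Working it through.** The Protocol gives no sample size, power or effect size, and this point depends on none. Two checks apply.

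**1. Does the ELISA reading depend on cell number?**

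Inputs from the sample preparation for ELISA: concentration c = 1.5×10⁶ cells/mL; 5 µL of supernatant plus 245 µL of buffer. Let N be the cells harvested and e the EGFR per cell, relative to control.

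- Lysis volume needed: V = N / c.
- EGFR in the lysate: N × e / V = c × e. N drops out.
- Dilution: (5 + 245) / 5 = 50-fold.
- Cell equivalents taken: 1.5×10⁶ per mL × 0.005 mL = 7,500. After dilution: 1.5×10⁶ / 50 = 30,000 per mL. Both are the same for every group.

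The surviving fractions and the 30% fall in EGFR below are illustrative assumptions, not figures from the Protocol. The last column shows, for contrast, a preparation with a fixed lysis volume, where the ratio to control is fraction × e.

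| Cells left, fraction of control | ELISA ratio as planned, e = 1 | ELISA ratio as planned, e = 0.7 | Fixed-volume ratio, e = 1 |
|---|---|---|---|
| 1.00 | 1.00 | 0.70 | 1.00 |
| 0.75 | 1.00 | 0.70 | 0.75 |
| 0.50 | 1.00 | 0.70 | 0.50 |
| 0.25 | 1.00 | 0.70 | 0.25 |
| 0.10 | 1.00 | 0.70 | 0.10 |

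The planned reading follows e and ignores the surviving fraction. If the MTT signal is taken as proportional to viable cells, and viability as 100 × (treated / control absorbance), the third row would read 50% viability by MTT next to an ELISA ratio of 1.00 when EGFR per cell is unchanged.

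The Protocol asks for a dilution of at least 50-fold. Unequal dilutions between groups would disturb the comparison but would not bring back information on cell number.

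**2. Do the places that define the outcomes agree?**

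| Item | PICO | Methods | Section 10 |
|---|---|---|---|
| Primary 1, name | Proliferative activity | Heading: proliferative activity; target: EGFR protein | EGFR expression |
| Primary 1, unit | Absorbance | Read at 450 nm | IC50, µg/ml |
| Primary 2, name | Apoptotic cell death | Fold change of four genes | Expression of four genes |
| MTT viability | Not listed | Described in full | Not listed |

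An IC50 needs a series of concentrations. The only µg/ml series in the Protocol is in the MTT steps; the ELISA text gives neither a concentration nor an exposure time for the coffee. The IC50 unit therefore fits the MTT assay and does not fit the ELISA as described.

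**The case against.** Several points on the other side are sound and limit the criticism.

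- **Normalising lysates is correct practice.** A reader might infer that fixing the cell concentration is itself a flaw. It is not: it is a proper way to compare EGFR expression between groups. Only the label is wrong.
- **Section 10 already uses nearly the right names.** The mislabelling lies in the PICO and the methods heading, so this part is a matter of reconciliation.
- **The IC50 unit may mean that MTT was intended to feed Primary 1.** One might conclude that the MTT data have no place in the conclusions at all. The text does not support anything so firm. Nor does it say that MTT supplies the IC50, since the named outcome and instrument are EGFR and an ELISA reader. Either way the role has to be written down.
- **MTT may not be the only cell-based read-out.** The sample preparation includes sulphorhodamine B staining with recovery of the stain, for which no outcome is assigned. It would be unsafe to call MTT the sole measure of viability.
- **MTT is also a proxy.** It does not separate slower growth from cell death, and exposure differs between assays: 48 h for MTT, 24 h for RT-PCR, unstated for the ELISA.
- **A harvest cell count is not a ready-made growth measure.** Reaching 1.5×10⁶ cells/mL implies counting, but a count shows growth only if seeding and exposure of those cultures are fixed, and the Protocol fixes neither.
- **The statistics section is descriptive only.** It has no rule for declaring a coffee anti-proliferative, and nothing forbids reporting MTT.

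What survives is that the PICO defines the primary outcome as something its assay does not measure, and that a fully described viability assay has no stated status. Both are matters this Protocol fixes itself; they are not details it leaves to an analysis plan.

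**Conclusion.** The concern holds as a mismatch between label and measurement, together with an undefined role for MTT. As prepared, the ELISA reads EGFR per cell and is insensitive to cell number: a 90% loss of cells with unchanged EGFR per cell leaves it at 100% of control. That result rests only on the stated lysate concentration and equal dilution across groups. The contrast with MTT also assumes a signal proportional to viable cells.

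The illustrative fractions show that the two quantities can diverge. A reader might take them as the size of the error to expect in this study, but the Protocol has no data on how EGFR and cell number move together, so neither the likelihood nor the size of a wrong conclusion can be estimated.

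The point is worth correcting before the results are written up, because it determines what the headline outcome means. It does not invalidate the assays.

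**What to change.** 1. In the PICO and the methods heading, rename Primary 1 as EGFR protein expression and Primary 2 as expression of apoptosis-related genes, to match Section 10. Correct the Section 10 line that places EGFR under apoptosis.
2. Add MTT viability at 48 h, as a percentage of control at each of the five concentrations, to both outcome tables as a named secondary outcome, with an IC50 per coffee if that is what the Section 10 unit means. Give the EGFR ELISA its own unit, the same in both tables. Define viability as 100 × the absorbance ratio, because the printed formula subtracts a proportion from 100: a ratio of 0.50 gives 100 − 0.5 = 99.5.
3. State that EGFR alone will not be reported as an anti-proliferative effect and that any such statement will be read together with the MTT result. Note that MTT does not separate slower growth from death, and give the exposure time of each assay, including the ELISA.
4. Say what the sulphorhodamine B steps are for, or remove them.

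This needs no new assay. The price is one more listed outcome and a more restrained claim. Secondary status is suggested because three coffees at five concentrations make 3 × 5 = 15 comparisons with control, which as primary outcomes would raise a multiplicity question that the Protocol does not address.

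### Primary 1 (EGFR by ELISA) is standardised only by cell concentration, with no viability criterion or total-protein normaliser, so cell death could be read as EGFR inhibition

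*Protocol*

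**What the plan says.** The PICO section of the protocol introduces the outcome as "Primary outcome 1: assessment of proliferative activity OSCC cell line treated with coffee using" ELISA. The table under 10. Outcomes names it as EGFR expression, with an IC50 in µg/ml as its unit. Under Measurement of proliferative activity the purpose is given: "Enzyme assay (ELISA) will be used to estimate the inhibitory effect green coffee, roasted coffee, decaffeinated coffee on" EGFR protein.

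Sample preparation for ELISA then sets the bench procedure:

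- Collection: "Cell lysis for cell culture samples will be carried by spinning down cells for 15 minutes at 1200 RPM".
- Washing: "Cell pellets are washed once in cold PBS".
- Standardisation: "Cells are re-suspended in Lysis Buffer to a concentration of 1.5x10⁶ cells/mL".
- Dilution: "The supernatant will be diluted at least 50-fold in 1X Assay Buffer", given as 5 µL of supernatant in 245 µL of buffer.

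The section names no viability count, dead-cell removal or total-protein measurement. Viability is assessed by MTT, which is described as a separate plate assay with no stated link to the ELISA lysates. Apoptotic cell death is Primary 2.

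**The concern.** A fixed cell concentration makes lysates comparable only if a counted cell means the same thing in every group. In a study that measures cytotoxicity and apoptosis, that cannot be taken for granted, because a treated pellet may hold a larger share of dead or leaky cells than a control pellet. If those cells are counted but carry less EGFR, EGFR per counted cell falls with no change in the living cells.

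The fixed dilution does not correct this, and nothing else in the ELISA section would reveal it. Primary 2 is expressed through ΔΔCT, a form that implies an internal reference; Primary 1 has no equivalent. At stake is whether a fall in Primary 1 can be attributed to EGFR at all, and whether a ranking of the three coffees on EGFR is partly a ranking on toxicity. This is bench procedure that the protocol itself fixes, not a detail normally left to a statistical analysis plan.

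**Working it through.** **The protocol's own figure.** The only checkable number in the ELISA section is the dilution: (5 + 245)/5 = 50-fold. It reproduces. It is the same for every lysate, so it leaves any difference in lysate content between groups unchanged.

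**Inputs to the size of the artefact**

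- Cells per mL: 1.5×10⁶, from the protocol, type of count not stated.
- *v*, the viable share of the counted treated cells: not in the protocol; assumed 0.5 to 1.
- *r*, EGFR in a dead cell relative to a live one: not in the protocol; assumed 0 to 1.
- True change in EGFR per living cell: set to none.
- Control pellet: fully viable (varied below).

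**Formula.** Treated/control EGFR per counted cell = *v* + (1 − *v*)*r*. Apparent inhibition = 1 − [*v* + (1 − *v*)*r*] = (1 − *v*)(1 − *r*).

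| Dead share 1 − *v* | *r* = 0 | *r* = 0.5 | *r* = 1 |
|---|---|---|---|
| 0% | 0% | 0% | 0% |
| 10% | 10% | 5% | 0% |
| 20% | 20% | 10% | 0% |
| 50% | 50% | 25% | 0% |

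The artefact therefore runs from nothing up to the dead share itself.

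**Some dead cells in the control.** With dead fractions dT (treated) and dC (control), apparent inhibition = 1 − [(1 − dT) + *r*·dT]/[(1 − dC) + *r*·dC]. Assume dC = 2-5%:

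- dT = 20%, *r* = 0: 1 − 0.80/0.95 to 1 − 0.80/0.98 = 15.8-18.4%.
- dT = 20%, *r* = 0.5: 1 − 0.90/0.975 to 1 − 0.90/0.99 = 7.7-9.1%.
- dT = 50%, *r* = 0: 1 − 0.50/0.95 to 1 − 0.50/0.98 = 47.4-49.0%.
- dT = 50%, *r* = 0.5: 1 − 0.75/0.975 to 1 − 0.75/0.99 = 23.1-24.2%.
- *r* = 1: 0% throughout.

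**Would a viable count repair it?** If the concentration is set by viable cells but dead cells stay in the lysate, treated/control = 1 + *r*(1 − *v*)/*v* against a fully viable control. At *v* = 0.5, *r* = 0.5 this is 1 + 0.5 × 1 = 1.50, an apparent 50% rise. With dC = 2-5% the ratio is 1.5/1.0263 to 1.5/1.0102, a rise of 46-48%, against the 23-24% fall being corrected. At dT = 20% it is 1.125/1.0263 to 1.125/1.0102, a rise of 10-11%, against a fall of 8-9%. It is exact only at *r* = 0.

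**Would total protein repair it?** Let *p* be total protein in a dead cell relative to a live one. EGFR per µg protein, treated/control, = [*v* + (1 − *v*)*r*]/[*v* + (1 − *v*)*p*]. If dead cells lose EGFR and other protein in proportion (*p* = *r*), this is 1 and the artefact disappears. If they keep all other protein (*p* = 1), nothing is gained over the count. If they lose other protein faster than EGFR (*p* < *r*), the error changes sign. Total protein helps so far as the two losses go together, which is why the viable fraction must be shown beside it.

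**The case against.** **The protocol is silent; it does not prescribe a total count.** A reader might infer that cells are counted whether alive or dead. The text does not say so. This stands, and the point is limited to the count type being unstated.

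**The bias is conditional.** A reader might infer that any cytotoxic coffee would show EGFR inhibition. That requires dead cells to be in the counted pellet and to hold less EGFR than live cells. If either fails, the artefact is zero. The ELISA section also gives no coffee concentration or exposure time, so the 20% and 50% dead shares are illustrations. This stands.

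**The harvest step is weak evidence.** Because the sample-preparation text says "Monolayer cells will be incubated for 48 hours" while the ELISA text goes straight to spinning, one might infer that only floating, mostly dying cells are collected. The monolayer sentence belongs to a 96-well procedure in which cells are fixed and stained, and nothing says those cells go to the ELISA. An unwritten detachment step is ordinary. On the literal reading, control pellets too would be mostly dying cells, which does not fit a control with 2-5% dead. What remains is that the handling of floating cells is unstated and affects the dead share.

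**No direction is hypothesised.** The research question is neutral, so it cannot be said that the artefact favours a stated hypothesis.

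**A fixed count is a legitimate choice.** It removes the plainer bias from having fewer cells in treated cultures, and MTT viability is already planned. Both are true. But the fixed count does not address the composition of the pellet, and the MTT result is not tied to the lysates in which EGFR is measured.

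**Conclusion.** The point holds in a limited form. Primary 1 is equalised by a cell concentration and a fixed dilution only, so a fall in EGFR cannot be separated from a larger share of dead cells in the pellet. With no true EGFR change, the artefact lies between 0% and about the dead share of the counted cells: 0-20% at 20% dead and 0-50% at 50% dead, against a fully viable control. The dead share and the EGFR retained by dead cells are both assumptions, and the protocol gives neither. The documents support a possible confounding of Primary 1 with cytotoxicity, not a demonstrated one. This is a cheap improvement to the stated standardisation, not an error that invalidates the plan.

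**What to change.** In Sample preparation for ELISA:

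1. Measure total protein in the same lysate and report EGFR per µg total protein as the Primary 1 value.
2. Record the viable fraction of each pellet by dye exclusion, at the count already needed to reach the stated concentration, and report it beside each EGFR value.
3. State one harvest rule for attached and floating cells and apply it in all four groups.

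Do not set the concentration by viable count while pooling dead cells into the lysate.

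The cost is a few protocol sentences, one routine protein reading and slightly more bench time per sample. Because protein normalisation does not fully remove the confounding, a fall in EGFR seen with a low viable fraction should be interpreted with caution.

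### Sections 7 and 8 rule out a sample size on two invalid grounds and leave the experimental unit and the number of independent runs unstated, so the planned mean and SD may show assay repeatability only

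*Protocol*

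**What the plan says.** Protocol section 7 (Calculated sample size): "No sample size estimation could be done, as the primary outcome is not a measured outcome". Section 8 (Description of study sample): "No sample size could be applied on cell line experiments as we generate millions of naturally randomized cells".

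The PICO outcome table gives Primary 1 (proliferation, by ELISA) the unit "Comparative (light absorbed) numerical value" and Primary 2 (apoptosis, by RT-PCR) the unit "Comparative (fold changes) numerical value". Section 10 again names an instrument for each. For Primary 1 it is the "Robonek P2000 ELISA reader", but the unit there is an IC50 in µg/ml. For Primary 2 the unit is a fold change.

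The aim is comparative. The Rationale sets out to assess the "activity of green coffee, in comparison to roasted coffee and decaffeinated coffee on cultured OSCC cell line", and the Intervention paragraph says "Oral squamous cell carcinoma cell line samples will be cultured with and without the addition of green coffee" (or of the other two extracts). Section D plans mean and standard deviation, or median and range, for numerical data. It names no test.

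**The concern.** A mean and SD can be read only when it is known what was repeated. Repeat wells of one culture vary because of pipetting and reading error. Independent runs vary also because of passage, day and, where extracts are prepared afresh, extract preparation. Only the second kind of spread shows whether a difference between coffees would recur.

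Sections 7 and 8 do more than leave the number open. They state that the question of sample size does not arise. A bench team following them could run one culture per arm, read several wells, report mean and SD, and be fully within protocol. The stated comparison of coffees would then have no replication behind it. A later analysis plan cannot repair that, because independent runs cannot be created after the bench work is finished.

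**Working it through.** **No figure to reproduce.** The protocol gives no sample size, power, effect size, SD or replicate number. The check is therefore of the two reasons, followed by an illustration.

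**Section 7 against the outcome tables.** Section 7 calls the primary outcome unmeasured. The PICO table and section 10 give both primaries a device and a numerical unit, and the ELISA steps end in a reading at 450 nm. The reason contradicts the document.

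**Section 8 against the methods.** Section 9 adds each extract to a group. What one measurement contains can be worked out from the protocol:
- MTT: 1 ml at 50,000 to 100,000 cells/ml is plated per well, as written, and absorbance is read per well. That is 50,000 to 100,000 cells for one number.
- ELISA (Primary 1): cells are lysed at 1.5 × 10⁶ per ml, and 5 µl of supernatant goes into 245 µl of buffer. 1.5 × 10⁶ × 0.005 = 7,500 cell equivalents in one diluted sample.
- RT-PCR (Primary 2): cells are harvested and lysed before testing.

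No cell is treated or measured singly, so millions of cells yield as many data points as there are wells or lysates. Independent information is limited further, to the number of separate cultures.

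**Replication stated elsewhere.** No section gives a number of wells, cultures, passages, runs or extract preparations.

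**Primary 1 unit.** An absorbance exists for every sample, including the control. An IC50 needs a dose series: each coffee gives one value per series and the untreated control gives none. The unit decides how many values there are to average.

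**Illustration 1: the SD (intraclass correlation, ICC, assumed).** If a share ICC of total variance lies between cultures, then within-culture SD / total SD = √(1 − ICC).
- ICC 0.1: √0.9 = 0.95
- ICC 0.2: √0.8 = 0.89
- ICC 0.5: √0.5 = 0.71

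**Illustration 2: if wells were later tested as independent (test, layout and ICC all assumed).** With one separate culture per arm and m wells each, the true rejection rate of a nominal 5% t-test is P(|t| > t_crit / √(1 + m·ICC/(1 − ICC))), with 2m − 2 degrees of freedom. For m = 3 and ICC 0.5, t_crit = 2.776 and the divisor is √(1 + 3) = 2, which gives P(|t₄| > 1.388) = 0.237.

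| m | ICC 0.1 | ICC 0.2 | ICC 0.5 |
|---|---|---|---|
| 3 | 0.074 | 0.104 | 0.237 |
| 6 | 0.115 | 0.189 | 0.419 |

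If both arms share the same culture effect, simulation gives 0.049 to 0.051, that is, no inflation.

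**Illustration 3: why the number of runs should be stated (all inputs assumed).** Take a difference of 1 cycle, SD 0.5, four groups in each run, 3(n − 1) degrees of freedom, SE = 0.5·√(2(1 − ρ)/n), and Bonferroni for the two comparisons in the Rationale. Power at three runs is 0.385, 0.685 or 0.976 for within-run correlation ρ of 0, 0.5 or 0.8. The answer depends almost wholly on ρ, which the protocol does not give. These are not recommended run numbers.

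**Which SD serves the comparison.** At SD 0.5 and ρ = 0.8, the across-run SD of one group is 0.50, while the SD of a within-run difference is 0.5·√(2 × 0.2) = 0.32. A blocked comparison needs the second.

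**The case against.** The strongest reply is that this is an in-vitro protocol that plans description only, that an analysis plan may exist, and that the Intervention paragraph speaks of samples in the plural, so independent cultures may well be intended. This stands in part. The harm is conditional, and a formal power calculation is not required: a justified number of independent runs would answer the point. It does not rescue sections 7 and 8, which assert wrongly that no number can apply.

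Four stronger readings are tempting and are not supported:
- **That the protocol takes cells as n.** Section 8 says only that a sample size cannot be applied. Nowhere is an SD computed over cells. The supportable claim is an invalid reason and no stated unit.
- **That natural randomization contradicts the statement "This study is non-randomized".** The first phrase can be read as describing mixing of cells in culture, the second describes assignment to groups. Both can be true.
- **That there is only one culture per arm.** The protocol neither says so nor excludes it.
- **That type I error is inflated.** No test is named, and inflation arises only from variation specific to an arm.

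The run-number illustration is also narrow. It covers one marker and two comparisons, whereas the primaries contain five markers (EGFR, Caspase-3, bax, bcl-xl, p53) and the untreated control implies further contrasts.

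**Conclusion.** The point holds. Both grounds for having no sample size are invalid on the protocol's own text, and no experimental unit or number of independent runs is fixed. These conclusions rest on the document alone.

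The consequence is conditional: if each arm is one culture, the planned mean and SD show assay repeatability and cannot support a comparison of coffees. Its size cannot be derived from the document. The SD ratios (0.95 to 0.71), rejection rates (7% to 42%, or 5% with a shared culture) and three-run power values are illustrations on assumed inputs.

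The two sentences, the unit and the number of runs should be settled before bench work starts.

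**What to change.** Delete the sentences in sections 7 and 8 and state instead:
- The experimental unit is one independent run: a separately passaged culture set containing all four groups. Wells and assay replicates are averaged to one value per group per run, and n is the number of runs.
- The across-run SD is reported for each group. For comparisons between coffees, the mean and SD of the within-run differences are reported, with gene expression on the ΔCT scale.
- The planned number of runs.
- Whether one extract stock per coffee is used throughout. If so, conclusions are limited to that stock.
- If only one run is done, that the SDs show assay repeatability only and support no claim of a difference between coffees.

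Reconcile the Primary 1 unit between the PICO table (absorbance) and section 10 (IC50). If IC50 is kept, there is one value per coffee per run and none for the control.

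Cost: mostly wording and run-level averaging. n becomes smaller, error bars will probably widen, and work must be scheduled across runs. Keeping a single run adds no work but gives up the comparative claim.
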